5.4.3. Reactogenicity (Solicited Adverse Events)

Solicited reactogenicity events are assessed at 30 (+/- 10) minutes following each vaccination and at home visits by field workers during the 6 days after each study vaccination. If more than one measurement is obtained on a given day (e.g. due to an unscheduled clinic visit) then the maximum level observed that day will be used in analysis. Note that per protocol, an event with onset on or after Day 7 post-vaccination is an unsolicited AE reported on the AE CRF.

Solicited REs will be tabulated for each assessment period (30 +/- 10 minutes and at each of the following 6 days) after each study vaccination. The percentage of subjects experiencing a grade 1+ or grade 3+ solicited RE in the 6 days following each study vaccination and across all 3 study vaccinations will also be tabulated, separately for local and systemic events.

The percentage of subjects experiencing grade 1+ REs (overall, any local RE, any systemic RE, and each individual event type) will be compared between PNEUMOSIL and the other treatment groups using 95% Miettinen-Nurminen Score-type CIs. If the event rate is 0% in both groups, then two event records – one for each group – will be included and given a weight of 0.000001 to facilitate computation of the 95% CI. Cochran-Mantel-Haenszel tests stratified on field site will be used to assess overall differences across the three groups (or Fisher's Exact tests if fewer than 5 events are observed in one of the treatment groups).

Any subjects with at least one Grade 3+ reactogenicity event post vaccination will be listed separately. For clinical context, the list will include all observations through Day 6 for that subject, reactogenicity endpoint, and vaccination.

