In the VAC-017 toddler cohort, 3 (5.4%) toddlers in the PNEUMOSIL group and 1 (1.8%) toddler in the Prevenar 13 group had severe TEAEs, and all had resolved. None of the severe TEAEs was considered related to study vaccine. The only severe TEAE reported for > 1 toddler was microcytic anemia, which was reported for 2 (3.6%) toddlers in the PNEUMOSIL group. There were 2 related TEAEs reported in the PNEUMOSIL group (Grade 1 diarrhea, Grade 2 morbilliform/papular rash) and 1 related TEAE in the Prevenar 13 group (Grade 1 pruritus). Two (2) treatment-emergent SAEs were reported, one in each treatment group and neither deemed related to study vaccine.

In the PCV10-002 study, only 1 (1.8%) toddler in the PNEUMOSIL group and 2 (3.5%) toddlers in Prevenar 13 group experienced severe TEAEs. None of the severe TEAEs was considered related to study vaccine. The only severe TEAE reported for > 1 toddler was anemia, which was reported for 2 (3.6%) toddlers in the Prevenar 13 group. There were 4 related TEAEs reported in the PNEUMOSIL group (Grade 1 diarrhea [2 events], Grade 1 AST increased, Grade 2 WBC count increased) and 3 related TEAEs in the Prevenar 13 group (Grade 1 AST increased, Grade 1 WBC count increased, Grade 2 WBC count increased). One subject in the PNEUMOSIL group and 2 subjects in the Prevenar 13 group had treatment-emergent SAEs during the study, none of which was deemed related to study vaccine.

In the VAC-017 infant cohort, the most common TEAEs reported in both treatment groups through 12 weeks post final primary vaccination included upper respiratory tract infection (64.0% PNEUMOSIL, 48.0% Prevenar 13), tinea infection (31.0% PNEUMOSIL; 21.0% Prevenar 13), diarrhea (29.0% PNEUMOSIL; 19.0% Prevenar 13), and conjunctivitis (27.0% PNEUMOSIL; 19.0% Prevenar 13). The most common TEAE after the booster vaccination through 4 weeks of follow up was upper respiratory tract infection (28.6% PNEUMOSIL, 12.8% Prevenar 13), dermatitis (8.2% PNEUMOSIL, 6.4% Prevenar 13), and diarrhea (4.1% PNEUMOSIL, 10.6% Prevenar 13). The differences in the frequency of these TEAEs between the treatment groups were within the expected range for this early-stage clinical study. The only vaccine-related TEAE for more than 1 infant was Grade 1 vaccination site swelling (2.0% PNEUMOSIL, 6% Prevenar 13), and the only severe TEAE reported for > 1 infant was bronchiolitis (2% PNEUMOSIL, 0% Prevenar 13).

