Field workers will be provided with a reactogenicity record form (RRF) for recording of reactogenicity events. The RRF will be retained as part of the source documents in the subject's file. The grading scales to be used for assessment of severity of local and systemic reactogenicity events are listed in Appendix 1 (Section 16.1). **Any Grade 3 or higher reactogenicity assessed by a field worker will result in immediate clinic contact, and the subject will be seen in the clinic within 24 hours of the event.** Field workers will contact the site to assist with scheduling if subjects are noted to be experiencing any medical condition (i.e., solicited or unsolicited AE) that needs to be evaluated by the PI at an unscheduled clinic visit.

Independent of a clinic visit, an RC will review the reactogenicity scoring with the field worker at the end of the 6-day assessment period, and sign off to confirm that this review has occurred. Following this review, an anonymized copy of the RRF will be submitted for data entry. If the condition of the RRF is such that data entry could be difficult, the source RRF could be transcribed to a new RRF for copying and submission. In this case the reason for this will be explained in the clinical notes. If more than 1 measurement of a particular parameter is taken and recorded, the value corresponding to the greatest magnitude of the RE will be used as the basis for categorizing and recording the event on the CRF during the given period of assessment. Any local or systemic reactogenicity or other AE ongoing at the day 6 home visit will prompt a day 7 follow-up visit in clinic. If a solicited AE is ongoing on day 6 post vaccination, or occurs after 6 days post vaccination, the event will be recorded on the AE CRF and continued to be followed as per AE monitoring requirements.

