9.2. Definitions

9.2.1. Adverse Event or Medical Event

- An AE is any untoward, undesired, or unplanned event in the form of signs, symptoms, disease, or laboratory or psychological/physiologic observations occurring in a subject enrolled in the clinical trial. This includes all subjects from whom consent has been obtained whether or not they have yet been randomized and received a study vaccine (PNEUMOSIL, Synflorix or Prevenar 13). The event does not need to be causally related to trial participation or receipt of a study vaccine. An AE is temporally related to participation in the study and will be documented as to whether or not it is considered to be related to vaccine. An AE includes, but is not limited to, the following:
 - An intercurrent illness or injury during the course of the study.
 - Any clinically significant worsening of a preexisting condition.
- A protocol-related AE is one that occurs from the time of enrollment until the EOS visit that is not considered to be related to receipt of the study vaccine, but is considered by the PI or the medical monitor (Sponsor or designee) to be related to the research conditions, i.e., related to the fact that a subject is participating in the study. For example, a protocol-related AE may be an untoward event occurring during blood sampling or other protocol-specified activity.
- A treatment-emergent AE is defined as an event that is not present prior to administration of the study vaccination, or, if present prior to the administration of the study vaccination, increases in intensity after administration of the study medication during the course of the study.

- Reactogenicity events include local and systemic reactions noted immediately post vaccination, or during follow-up visits through day 6 after study vaccine administration by field workers and confirmed by the PI.
 - Any solicited AE that is ongoing on day 6 post study vaccine administration, or occurs after 6 days post study vaccine administration will be entered as an unsolicited AE and followed in line with the follow-up for other unsolicited AE.

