5.4.2. Adverse events

The onset date will be compared to the date of 1st vaccination (Day 0) to determine if it is a TEAE. Adverse events are considered treatment emergent if (a) onset occurs on or after the date/time of first vaccination, or (b) an event with onset prior to the first vaccination but increases in severity after administration of the vaccination. Only TEAEs with onset on or before V6 (4-weeks post booster) will be included in the formal safety analysis, although listing will be provided of all other AEs that occur in subjects who are not in the Safety Population or are not treatment emergent.

Summary tables of TEAEs (overall and by onset within 28 days of each vaccination) will be presented with numbers of events, and numbers and percentage of subjects, with any: (a) TEAEs; (b) unexpected TEAEs; (c) serious TEAEs; (d) vaccine-related TEAEs; (e) vaccine-related SAEs; (f) TEAEs leading to discontinuation of the vaccination series; and (g) TEAEs leading to death. Treatment-group differences in percent of subjects will be compared for each category (a)-(f) using the Cochran-Mantel-Haenszel (CMH) test stratifying on field site (Fisher's exact tests will be used if the number of events is < 5 for at least one treatment group). The 95% CI around treatment-group differences (PNEUMOSIL versus each comparator) will also be reported using Miettinen-Nurminen Score-type intervals (if the event rate is 0% in each group, then two event records – one for each group – will be included and given a weight of 0.000001 to facilitate computation of the 95% CI).

The process for medical coding will be conducted according to the █ 360 SOP 06006 “Medical Coding of Clinical Study Data using MedDRA”. Unsolicited TEAEs will be summarized and grouped by MedDRA System Organ Class (SOC) and AE preferred term using MedDRA™ v22.0 or higher coding terminology, by treatment group and pooled across groups. A similar summary will be provided for non-serious TEAEs (pooling solicited and unsolicited events). Results will be displayed in order of decreasing frequency, both across SOC and within each SOC term. In addition, TEAE summaries will be provided by severity (mild, moderate, severe, or life threatening/death if any), and by relationship to study vaccine (Related, Unrelated), overall and according to onset within 28 days of each vaccination.

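### SAP 5.4.3 leaves out the protocol's rule for solicited reactions still ongoing on Day 6, so one reaction can be counted twice in the event counts of the pooled non-serious TEAE summary

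*SAP*

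**What the plan says.** The protocol states its rule twice. Section 7.1.2 (home visits) reads: "If a solicited AE is ongoing on day 6 post vaccination, or occurs after 6 days post vaccination, the event will be recorded"; the form it names is the AE CRF. Section 9.2.1 sets the same two conditions and says that a reaction meeting either one "will be entered as an unsolicited AE and followed in line with the follow-up for other unsolicited AE". There are two routes onto the AE CRF: the reaction persists to Day 6, or it begins later. Section 9.2.1 also defines local and systemic reactions seen through Day 6 as reactogenicity events (REs).

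SAP 5.4.3 restates the rule with one route: "Note that per protocol, an event with onset on or after Day 7 post-vaccination is an unsolicited AE reported on the AE CRF". SAP 5.4 defines solicited events found at the 30-minute check or in the first 6 days as REs, and separates them from all remaining AEs, which it calls unsolicited.

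SAP 5.4.2 plans a summary of unsolicited TEAEs by system organ class and preferred term, and then adds: "A similar summary will be provided for non-serious TEAEs (pooling solicited and unsolicited events". Protocol 12.8 requires safety tabulations to give both the number of events and the number and percentage of subjects.

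Protocol 9.2.3 says that solicited REs are not assessed for relatedness. Under 9.2.7, events on the AE CRF are.

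**The concern.** The SAP cites the protocol as the source of its note, so a programmer would reasonably take it as the whole rule and assume that the RE and AE datasets do not overlap. They do overlap. A swelling that starts on Day 1 and is still there on Day 6 appears in the daily RE records and again as an AE. If the two sources are stacked for the pooled non-serious summary on the assumption of no overlap, that swelling adds two events.

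The second effect is on interpretation. Once on the AE CRF, a persistent reaction receives a relatedness judgement that it would not have had as an RE, so it can enter the vaccine-related TEAE rows. The protocol intends that entry. The SAP, however, gives the reader no way to tell a persisting injection reaction from a new event. Solicited AEs, and unsolicited AEs with their relatedness, are separate primary safety endpoints, so the boundary between them should be explicit.

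**Working it through.** The documents give no figure for this issue, so the check is a comparison of texts followed by an illustration of size.

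**Step 1: trace three reactions through both documents.**

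| Reaction | Protocol 7.1.2 and 9.2.1 | SAP 5.4 and 5.4.3 |
|---|---|---|
| Starts Day 1, gone by Day 3 | RE only | RE only |
| Starts Day 1, still present on Day 6 | RE, and unsolicited AE on the AE CRF | RE; crossover to the AE CRF not mentioned |
| Starts Day 8 | Unsolicited AE | Unsolicited AE |

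The documents agree on the first and third rows. They part on the second, which is the only case with two records.

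**Step 2: look for a rule that resolves the second row.** Neither document links the RE and AE records, says which is counted when the sources are pooled, or says whether the AE entry carries the original onset date or a later one. The table shells are kept outside the SAP (sections 1 and 6) and are not available.

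**Step 3: find which outputs are affected.**

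- Pooled non-serious TEAE summary (SAP 5.4.2): the event count can rise by one for each carried-over reaction. The subject count for a preferred term does not change if both records code to that term.
- RE tables (SAP 5.4.3): unaffected.
- Unsolicited and vaccine-related TEAE tables (SAP 5.4.2): a carried-over reaction appears once, as the protocol prescribes. A subject whose only qualifying AE is a carry-over is added to the row.

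**Step 4: illustrate the size.** Let R be the number of reactions of one type in an arm, one per reacting subject, and f the share still ongoing on Day 6. The documents do not give f; 1% to 10% is assumed. Duplicates = R × f, with 220 subjects per arm.

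- Assumed 50% reaction rate: R = 220 × 0.50 = 110. Duplicates = 110 × 0.01 = 1.1 to 110 × 0.10 = 11, so 110 events become 111.1 to 121. Subjects also appearing in the unsolicited table: up to 1.1/220 = 0.5 to 11/220 = 5.0 percentage points.
- Assumed 10% reaction rate: R = 22. Duplicates = 0.22 to 2.2, so 22 events become 22.22 to 24.2. Subjects also in the unsolicited table: up to 0.1 to 1.0 percentage points.

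In each case the pooled event count rises by the fraction f. Protocol 1.8.1 reports that most REs in earlier infant cohorts resolved within 24 to 48 hours, which suggests a small f but does not give it.

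**The case against.** The strongest reply is that the SAP sentence is true as far as it goes: an onset on or after Day 7 is indeed an unsolicited AE under the protocol. A reader might infer that the SAP admits no other route, but the sentence does not say so. It is an incomplete restatement and does not change what sites enter. That stands.

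A reader might also infer that the SAP prescribes counting twice. It does not. Under the definition in SAP 5.4, a Day 1 reaction could be classed once, as an RE. That stands too, but it does not settle the matter: counting it only as an RE would set aside a record that the protocol calls an unsolicited AE, and no SAP rule authorises that.

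The reach is narrow. Pooling is stated for one descriptive summary. The planned between-group comparisons use percentages of subjects, and SAP 5.4.1 treats any tests as a guide only. The entry rule is the same in all three arms. So duplicate events within the pooled table should not alter a planned comparison, provided that both records code to the same term.

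It may also be said that a longer-lasting reaction appearing as a related AE is real tolerability information. That is right, and it is a reason to keep these events in the unsolicited and related tables. Removing them would conflict with the protocol's entry rule and with an endpoint that covers every unsolicited AE.

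Finally, it is tempting to size the problem from earlier trials. For VAC-017 infants, Protocol 1.8.1 says: "The only vaccine-related TEAE for more than 1 infant was Grade 1 vaccination site swelling" (2.0% PNEUMOSIL, 6% Prevenar 13). In VAC-056 vaccination-site swelling was the most common related TEAE (0.3% PNEUMOSIL, 0.7% Synflorix). Scaled to 220 per arm, these give 220 × 0.003 = 0.7 to 220 × 0.06 = 13.2 subjects, and a reader might conclude that carry-overs make up most of the vaccine-related row. The documents do not support that: they do not say how many of those events were carry-overs, or whether those trials used this rule.

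**Conclusion.** The concern holds in a limited form. SAP 5.4.3 gives an incomplete account of the protocol's rule, omitting solicited reactions still ongoing on Day 6. Those reactions are held in both sources, and SAP 5.4.2 pools the sources in one summary without a linking rule. Double counting of events in that summary is therefore possible and unprevented, though not prescribed. In the unsolicited and vaccine-related rows the fault is only that carried-over reactions cannot be identified; their presence follows from the protocol.

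The number affected is unknown and probably small. The 1% to 10% illustration rests on an assumed share ongoing on Day 6. The statement that subject percentages are unaffected rests on both records coding to the same preferred term; the SAP does not say how REs are mapped to terms for pooling. The table shells might already handle the overlap, but they cannot be seen. This is a clarification worth making because it can change a reported count, not a threat to the trial's safety conclusions.

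**What to change.** 1. Amend the note in SAP 5.4.3 to match Protocol 7.1.2 and 9.2.1: a solicited reaction goes on the AE CRF if it is ongoing on Day 6 or begins later.
2. In SAP 5.4.2, state that the AE record of a carried-over reaction is linked to its RE by subject, dose and reaction term, and state which onset date applies.
3. Count each linked pair once in the pooled non-serious TEAE summary.
4. Keep carried-over events in the unsolicited and vaccine-related tables, flag them, and show their number by dose and arm.

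The cost is a few lines of SAP text, one derived flag and a little programming. No new data are needed.

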5.4.4. Vital signs

Vital signs (temperature, resting respiration rate and resting pulse rate) will be presented in listings and summarized via standard descriptive statistics as well as by protocol severity (toxicity) grades for each treatment group and measurement time point (pre-vaccination, 30

minutes post vaccination, scheduled follow-up visit). Data from subjects with Grade 2+ vital signs at any time, including unscheduled visits, will be listed separately.

6. TABLES, LISTINGS, AND FIGURES

Planned TLFs intended to capture interim and final analyses described in the SAP are reviewed by the Sponsor before going into production. Since numbering and other formatting of the TLFs will change during the analysis, review, and CSR writing process, and because additional TLFs may be created for exploratory analyses not anticipated prior to un-blinding, the TLF shells are maintained separately from the approved version of the SAP.

6.1. Programs and Tables Quality Control

Report production and review will be conducted in accordance with [REDACTED] BIOS Work Instructions (WI) 03003 (Verification of Analyses and Reports) and 03006 (Preparation and Review of Statistical Reports). In brief, a primary statistician-programmer for a given output will carefully review the program and output, verifying that no error message is highlighted in the “LOG” file and that titles, footers, footnotes, text body, etc. are correct. A second statistician-programmer will independently validate the output by checking the results against separately created SAS programs and checking textual material. Prior to delivery of any statistical output to Sponsor, the lead statistician will review the statistical package for internal inconsistencies or any items where clarifying notes will be helpful to the reviewer. The package is then thoroughly reviewed by the Biostatistics Director or designee before it is distributed.

6.2. Programming Conventions

Reporting conventions will adhere, when possible, to the International Conference on Harmonization Guidance document E3, “Structure and Content of Clinical Study Reports”.

All tables and listings will be in landscape format unless otherwise requested.

Each table/figure/listing will have at least three titles:

- The 1st title will have the study/report name
- The 2nd and as needed 3rd titles will be the TLF number and description, and will identify the objective being addressed
- The last title will identify the study population

Each table/figure/listing will also identify:

- Date of data freeze
- Data source (analysis data set)
- Listing source (associated listing, if any, for further details)
- File reference (name of output file)

- Run date

All SAS output for tables and listings will be distributed in PDF files, with RTF files created for inclusion into the CSR or sponsor presentations.

8. APPENDIX

8.1.1. Changes to Analysis Plans after Approval of Protocol Version 1.0

- In the event of any randomization errors, supportive analyses based on the Full Immunogenicity Population will be performed according to randomized treatment assignment, rather than treatment received at enrolment. This change was implemented in Version 1.0 of the SAP, prior to any unblinding of any study team members.
- The SAP was updated throughout to reflect the change in the timing of clinic visits in response to the COVID-19 pandemic and related changes to the definition of safety endpoints (Section 2.2.1), procedures for selecting subjects contributing to OPA analysis (Section 3.5), the use of covariates (Section 3.9) in sensitivity and exploratory analyses of immunogenicity data (Sections 5.3.7 and 5.3.8), and the reporting of unsolicited TEAEs with onset after month 9 of age but before V5 (Section 5.4.2). These modifications to the SAP were made blind to individual patient treatment group assignments.
- The SAP was updated (V3) to provide further details regarding non-random selection of subjects for OPA analysis (Section 3.5) and to provide additional details regarding TEAE summaries (5.4.2). These modifications to the SAP were made blind to individual patient treatment group assignments.
- The SAP was updated (V4) to address a change in reports on timing of AE onset in relation to each vaccination (from 14 days to 28 days). Version 4 also clarified that unblinding of non-immunogenicity analyses may occur before immunogenicity results are available due to laboratory delays arising from the COVID-19 pandemic.
- The SAP was updated (V5) to address issues that arose in blind review of data. The decision was made to compare rates of REs between groups using 95% CIs for differences in proportions (rather than p-values) to be consistent with AE summaries. Also specified in the updated SAP is how to report 95% CIs when the response rate is 0% or 100% in both groups being compared, since SAS PROC FREQ does not report a result in this case.
